# 5. RESEARCH QUESTION AND OBJECTIVES

#### **Research question:**

This study aims to address Takeda's EU RMP commitment to assess the safety of maribavir in patients with ESRD and patients with severe chronic renal disease requiring peritoneal dialysis or hemodialysis. The research question is:

• What is the safety profile of maribavir for treating post-transplant CMV infection in patients with ESRD or severe chronic renal disease requiring peritoneal dialysis or hemodialysis?

#### **Primary objective:**

• To characterize the safety of maribavir as prescribed in routine clinical practice in terms of occurrence of AEs in patients with post-transplant refractory CMV infection and comorbid ESRD or comorbid severe chronic renal disease requiring peritoneal dialysis or hemodialysis.

#### Secondary objective:

To assess the occurrence of AESIs:

- Immunosuppressant drug concentration level increased
- Tissue-invasive CMV disease
- Relapse or progression of the underlying disease for which the transplant was performed
- Taste disturbance (dysgeusia)
- Nausea
- Vomiting
- Diarrhea
- Invasive fungal or bacterial infections
- GVHD

# 6. **RESEARCH METHODS**

#### 6.1 Study Design

This is an observational, multicountry, retrospective, post-authorization safety study (PASS) based on the secondary data collected from medical records of transplant recipients treated with maribavir who are refractory to prior anti-CMV treatment and are diagnosed with ESRD or severe chronic renal disease requiring peritoneal dialysis or hemodialysis.

The study does not interfere with standard medical care and will not impact the current treatment of the study participants.

Physicians will be asked to screen existing medical records and consecutively include eligible patients until the study meets the expected sample size. Chart reviews will be performed regardless of the patients' survival status at the time of initiation of data abstraction.

The study design will include a study follow-up period covering the full duration of the treatment course with maribavir from index date (Day 0: the day of initiation of the first maribavir treatment course during the eligibility period) until death, end of data availability, end of treatment or treatment discontinuation +7 days post-treatment, whichever occurs earliest. An additional 7-day grace period following treatment discontinuation or end of treatment is allowed to capture potentially relevant events that may occur in the immediate period after the censoring event.

Eligibility period is defined as the period of time within which the index date must fall for the patient to be included in the study. Index date should have occurred between the commercial launch date of maribavir and 3 months before the first data abstraction. These dates will be different for each country. Data collection will span 2 main periods of time anchored to the date of index event:

[figure not shown]
- Pre-index event period: begins on the date of diagnosis of kidney disease or underlying health issue that leads to the transplant and ends 1 day before the index date during the eligibility period
- Post index event period: begins on 1 day after the index date during the eligibility period and ends at the earliest of death, completion of maribavir treatment+7 days post-treatment completion, maribavir discontinuation for any reason+7 days post-treatment, or end of data availability

Data from the patient's medical records will be abstracted by study investigators routinely involved in the care and treatment of the target indication (or delegates at the study site). Pseudoanonymous patient-level data will be transcribed, onto electronic case report forms (CRFs) to capture (i) baseline characteristics during the pre-index event period (eg, demographics, comorbidities, disease characteristics, treatment history) and (ii) follow-up data during the post index event period (eg, treatment patterns and safety events).

The primary endpoint is the incidence of any AE. The secondary endpoint is the incidence of the AESIs. The primary and secondary endpoints will be collected as part of the safety events in the post index event period. More details on the study endpoints are provided in Section 6.7.

Before study commencement, the protocol and relevant study documents approval will be obtained from an institutional review board (IRB) or ethics committee (EC). Participants must provide written informed consent before their inclusion in the study, as applicable. IRB/EC approval of a waiver of informed consent will be sought to allow record reviews of deceased patients.

A study design schematic is presented in Figure 1.

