#### 02 June 2023

The study design will include a follow-up period covering the full duration of the treatment course with maribavir from the index date (Day 0: the day of initiation of the first maribavir treatment course during the eligibility period) until the earliest of death, end of data availability, treatment discontinuation, or end of treatment+7 days post-treatment. An additional 7-day grace period following treatment discontinuation or the end of treatment is allowed to capture potentially relevant events that may occur in the immediate period after the censoring event.

The eligibility period is defined as the period of time within which the index date must fall for the patient to be included in the study. The index date should have occurred between the commercial launch date of maribavir and at least 3 months before the first data abstraction. These dates will be different for each country. Data collection will span 2 main periods of time anchored to the date of the index event:

- Pre-index event period: begins on the date of diagnosis of kidney disease or underlying health issue that leads to the transplant and ends 1 day before the index date during the eligibility period
- Post index event period: begins 1 day after the index date during the eligibility period and ends at the earliest of death, completion of maribavir treatment+7 days post-treatment completion, maribavir discontinuation for any reason+7 days post-treatment discontinuation, or the end of data availability

The primary endpoint is the incidence of any AE. The secondary endpoint is the incidence of an AESI.

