# 6.4.2 Variables to Address Study Outcomes

Safety data will be collected during the index and post index period, including days after the completion of maribavir treatment or treatment discontinuation. The primary outcome is the incidence of AEs. The secondary outcome is the incidence of AESIs.

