# 6.7.1 Statistical Methods

Unless otherwise specified, all statistical analyses will be descriptive in nature. Continuous variables will be described by the number of eligible participants and missing data, mean, standard deviation, median, first quartile, third quartile, and minimum and maximum values. Categorical variables will be described as the total number of participants and relative percentage per category. Percentages will be calculated using the most appropriate denominator. Two-sided 95% CIs will be reported as appropriate.

Should missing data occur, missing data will not be imputed and the data will be analyzed as they are recorded in the study eCRFs. However, for all missing dates, some date imputation may be performed. The general imputation rules will be described in the SAP. Missing data may be included as a separate category in some cases, depending on the nature of the variable. Unless otherwise specified in a table's footnote, missing values will not be included in the denominator for summarizing a categorical variable's distribution. If the eCRF includes a selection of "unknown," these responses will not be considered missing responses and will be included in the distributions.

Descriptive analysis will be performed on the variables listed in Section 6.4. Year of birth will be analyzed as age and age group, and dates would be as duration or index days/weeks. Detailed definitions of additional variables that may be derived from the collected data for the statistical analysis will be included in a separate SAP.

Incidence of each outcome will be expressed per person-year of exposure to account for varying length of follow-up. Incidence rates will be calculated as the number of patients with an event of interest, divided by the number of person-years at risk, ie, the summed person-year of maribavir exposure. Only new cases will be included in the numerator; patients with existing AEs at the index date who reported the AE before the index date will not be counted, and patients who initially experience AEs at index or at the post index date will be counted only once in the numerator (ie, worsening outcomes will not be counted as new cases). The following definitions will be used to estimate incidence rates:

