- Person-days at risk for an individual will be defined as the total number of days of maribavir exposure (ending at the date of the outcome of interest, the final dose of maribavir +7 days, death, or end of data availability). For each incidence rate, 95% CIs will be calculated using exact methods.
- The follow-up period (person-days) will be defined as the period from the index date until the earliest of: 7 days following the date of discontinuation of initiated maribavir medication, end of data availability, or death.
- Person-years will be calculated by dividing person-days by 365.

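### The protocol contradicts itself on whether adverse events starting on the first day of maribavir fall inside the endpoint collection window

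*Protocol*

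**What the plan says.** Section 6.1 starts follow-up "from index date (Day 0: the day of initiation of the first maribavir treatment course during the eligibility period"). The same section then divides data collection into two main periods around that date. The pre-index period "ends 1 day before the index date during the eligibility period". For the other it states: "Post index event period: begins on 1 day after the index date during the eligibility period". The abstract, under Study Design, repeats this: "Post index event period: begins 1 day after the index date during the eligibility period".

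Section 6.1 next assigns content to the periods. Baseline characteristics belong to the pre-index period; treatment patterns and safety events belong to the post-index period. On the endpoints it says: "The primary and secondary endpoints will be collected as part of the safety events in the post index event period".

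Other sections treat Day 0 differently:

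- Section 6.4 lists three collection periods: pre-index, index and post-index.
- Section 6.4.2: "Safety data will be collected during the index and post index period".
- Section 6.7.1, numerator: "patients who initially experience AEs at index or at the post index date will be counted only once in the numerator".
- Section 6.7.1, time at risk: "The follow-up period (person-days) will be defined as the period from the index date".
- Abstract, Data analyses: incidence covers events from the index date, identified there as the start of maribavir.

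**The concern.** The primary endpoint is the incidence of any AE and the secondary endpoint is the incidence of AEs of special interest (AESIs). Both depend on which onset dates are abstracted from the chart. If the abstraction guide or the eCRF date checks are built from 6.1, an AE starting on the first treatment day has no period to be entered in. It is too late for the pre-index period and too early for the post-index period.

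The analysis cannot recover an event that was never entered. Nor would a reaction that starts on Day 0 and persists come back later as a new case, because Section 6.7.1 does not count worsening as new. The denominator would still begin on Day 0, so events and time at risk would start on different days.

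Four of the nine AESIs are taste disturbance, nausea, vomiting and diarrhea, which Section 4 names among the most common AEs in the earlier studies. The protocol does not say how soon after the first dose they begin.

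**Working it through.** **1. Is Day 0 inside the window?** With the index date as Day 0:

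| Place | Rule | Day 0 included? |
|---|---|---|
| Abstract (Study Design) and 6.1, pre-index period | ends Day −1 | no |
| Abstract (Study Design) and 6.1, post-index period | starts Day +1 | no |
| 6.1, endpoint collection | in the post-index period | no |
| 6.1, follow-up | starts Day 0 | yes |
| 6.4, variables | pre-index, index, post-index | yes |
| 6.4.2, safety data | index and post-index | yes |
| 6.7.1, numerator | AEs at index counted | yes |
| 6.7.1, person-time | starts on the index date | yes |
| Abstract, Data analyses | events from the index date | yes |

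The period definitions and the endpoint sentence in 6.1 exclude Day 0; every other rule includes it. Section 6.1 also disagrees with itself, because its follow-up starts on Day 0.

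**2. The plan's own figures.** No figure in the protocol depends on the index-day rule. Table 3 gives the precision context. Its intervals are exact (Clopper-Pearson): lower limit = 0.025 quantile of Beta(x, n−x+1), upper limit = 0.975 quantile of Beta(x+1, n−x). With n = 10 and x = 5 this gives 18.7% to 81.3%, width 62.6 points, as stated. All 14 cells reproduce to 0.1 point.

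**3. Size of one missed patient.** The target is about 10 patients (Section 6.5), so one patient is 1/10 = 10 percentage points.

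**4. Illustration.** Assumptions: 10 patients; 8 weeks of treatment, borrowed from the Phase 3 trials described in Section 4, plus 7 days, so 56 + 7 = 63 days each; 5 patients with a first event, one of them on Day 0; for simplicity, time is not stopped at the event.

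- Person-years: 10 × 63 / 365 = 1.726.
- All 5 counted: 5/10 = 50% (95% CI 18.7 to 81.3); rate 5/1.726 = 2.90 per person-year (exact 95% CI 0.94 to 6.76).
- Day 0 event not abstracted: 4/10 = 40% (12.2 to 73.8); rate 4/1.726 = 2.32 (0.63 to 5.93).

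**5. Denominator share of Day 0.** Under the same assumption it is 1/63 = 1.6% of person-time. It is 1/14 = 7.1% for one week of treatment plus 7 days, and 1/175 = 0.6% for 24 weeks plus 7 days. At the assumed 8 weeks the stake is therefore in the numerator.

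**The case against.** The best defense is that 6.1 should not be read alone. Its endpoint sentence does not say *only*, and the next one sends the reader to Section 6.7, where events at index are expressly counted. Section 6.4.2, which governs the outcome variables, includes the index day. Section 6.4 treats index as a collection point of its own, and 6.4.3 to 6.4.5 are organized that way. Under the analysis rules, numerator and denominator both begin on Day 0.

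This stands. A reader of 6.1 might infer that endpoints are collected only after Day 0 and that first-day events are lost. The documents do not support that, because several sections expressly include those events. The defense does not remove the contradiction, however. Section 6.1 is where the protocol assigns safety events to an eCRF period, and Section 6.8.1 plans date-range checks at entry, so the wrong wording could reach the collection tool.

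Two further inferences also fail:

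- A reader might think that an AE before the first dose on Day 0 would count. Sections 6.7.1.1 and 6.7.1.2 limit the rates to events after administration, which largely answers this.
- A reader might think that a Day 0 event contributes no person-time. Section 6.7.1 counts days of exposure, and Section 6.7 leaves derivations and censoring to the SAP, so the day-count convention is not a defect here.

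The total event counts in 6.7.1.1 and 6.7.1.2 offer no protection, since an event that was not abstracted is missing from those too.

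**Conclusion.** The contradiction is real and concerns the collection window for the primary and secondary endpoints. The abstract's Study Design text and 6.1 exclude Day 0; the abstract's Data analyses, 6.4.2 and 6.7.1 include it. The consequence is conditional: Day 0 AEs could be missed if sites or the eCRF follow 6.1, with Day 0 still in the denominator.

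Each patient missed moves a proportion by 10 points at the planned size. How many would be affected cannot be derived, because the protocol has no onset-time data. The drop from 50% to 40% shows the scale for one patient and is not a forecast. It is also small beside the sampling uncertainty, with an interval 62.6 points wide at 50%. The point merits correction because it is avoidable and the study is too small to give up events it intends to count.

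**What to change.** - In the abstract (Study Design) and in Section 6.1, start the post-index (risk) period on the index date, from the first maribavir dose. The pre-index period can still end the day before.
- In the endpoint sentence of Section 6.1, refer to the index and post-index period, so that it matches Sections 6.4.2 and 6.7.1.
- Carry the same window into the eCRF completion guidelines and the date-range edit checks.

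No analysis rule, sample size or precision figure changes. Appendix A lists the data management plan as still to be developed, and Section 6.6 has it approved before the database design is final. Made before database build, the change costs only wording. Made after the first extraction wave, it could mean returning to charts for Day 0 events.

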## Figure 1Study Design Schematic

# 6.2 Setting

## 6.2.1 Study Population

This study aims to include approximately 10 adults treated with maribavir for a refractory CMV infection and who have comorbid ESRD or severe chronic renal disease requiring peritoneal dialysis or hemodialysis. The current study involves a review of routine clinical information available in the medical charts of eligible patients before the study start.

To ensure representation of several European regions, and based on maribavir launch and market uptake, the proposed study countries may include Austria, Belgium, Denmark, Estonia, France, Germany, Italy, Spain, and United Kingdom.

# 6.2.2 Inclusion Criteria

Eligible patients must have the following attributes documented in the medical record at the time of enrolment to be included in the study:

- Adults  $\geq 18$  years of age at index date
- Diagnosis of ESRD or severe chronic renal disease prior to the index date
  - If ESRD: patient diagnosed with ESRD confirmed by an eGFR <15 mL/min
  - If severe chronic renal disease: patient diagnosed with severe chronic renal disease requiring peritoneal dialysis or hemodialysis; patient has an eGFR of 15 to <30 mL/min at index
- Patient has undergone SOT or HSCT before index date
- Patient was diagnosed with refractory (with or without resistance) CMV during the latest post-transplant period
- Patient initiated treatment with maribavir in routine practice within the eligibility period and received at least 1 dose of maribavir
- Informed consent provided (where required by local regulations) before data collection commences

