To date, evidence of maribavir safety is lacking in patients with post-transplant refractory CMV infection and either an eGFR <15 mL/min or an eGFR <30 mL/min receiving peritoneal dialysis or hemodialysis, and this is considered missing information in the European Union (EU) Risk Management Plan (RMP) (Takeda 2022, EU Risk Management Plan (RMP) for Livtencity (Maribavir) V0.7).

This observational (noninterventional) study is designed to assess the safety of maribavir for the treatment of refractory CMV infections in HSCT and SOT recipients among patients with ESRD and patients with severe chronic renal disease requiring peritoneal dialysis or hemodialysis in real-life conditions in the post-commercialization phase, as reported by the treating physicians. This study will also evaluate the occurrence of adverse events of special interest (AESIs), which have been recorded in the SHP620-303 trial protocol (Avery et al. 2022).

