## 6.2.3 Exclusion Criteria

There are no exclusion criteria for this study

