#### 02 June 2023

- Current CMV infection
  - Date of onset of infection/diagnosis
  - Refractory characteristics
    - Antiviral agent to which CMV infection is refractory
    - Type of drug-resistant mutations (if applicable)
  - Agent that patient is refractory to
  - o Classification of CMV infection
    - Asymptomatic
    - Tissue-invasive CMV disease
    - CMV syndrome
  - Prior anti-CMV medication used to treat the current CMV infection
    - Induction and maintenance therapy received for transplant, rejection treatment, and other adjuvant/related therapy
    - Start/end dates
    - Other anti-CMV prophylaxis and treatment
    - Other anti-infective agents
  - AEs including renal toxicity from prior anti-CMV treatment
- Current transplant status
  - Date of transplant
  - Type of transplant
    - HSCT
      - Autologous
      - Allogeneic
    - SOT
      - Heart transplant
      - Lung transplant
      - Liver transplant
      - Pancreas transplant
      - Intestine transplant
      - Kidney transplant
      - Other transplant
  - Reason for transplant
    - Leukemia (acute myeloid)
    - Leukemia (chronic myeloid)
    - Leukemia (acute lymphocytic)
    - Lymphoma (non-Hodgkin's)
    - Myelodysplastic syndrome
    - Other myeloid malignancy
    - Other
  - Stem cell source (for HSCT)
    - Bone marrow
    - Peripheral blood stem cell
    - Cord blood
    - Other

02 June 2023

- o CMV serostatus
  - Donor positive/recipient positive
  - Donor negative/recipient positive
  - Donor positive/recipient negative
  - Donor negative/recipient negative
- Current GVHD status (for HSCT patients only)
  - Acute GVHD status
    - Presence
    - Absence
    - Grade
  - Chronic GVHD status
    - Presence
    - Absence
    - Grade
- Relevant comorbidities ongoing or diagnosed at index date and treatment

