# 6.5 Study Size

The source population for the current PASS comprises of post-transplant patients with CMV infection/disease refractory (with or without resistance) to prior antiviral treatments and a post-transplant diagnosis of comorbid ESRD or comorbid severe chronic renal disease requiring peritoneal dialysis or hemodialysis. As such, study size will be dependent on the patterns of use of maribavir in routine clinical practice during the first years after launch for an indication that is expected to be ultra rare.

Considering the eligibility criteria, coupled with the rarity of the source population, the target sample size for this PASS is approximately 10 patients. This target sample size was determined by practical and feasibility assessments, and findings from the pivotal SHP620-303 (SOLSTICE) trial. Of the 352 randomized patients in the SOLSTICE trial, only 11 patients with 8 (2.3%) on maribavir treatment had severe chronic renal disease, defined as creatinine clearance <30 mL/minute according to the Cockcroft-Gault formula (Avery et al. 2022; Sampson and Drury 1992). Notably, patients in the SOLSTICE trial were not on dialysis; the current study aims to further select patients from an already rare population. Although no formal hypotheses have been prespecified and sample size calculations are not applicable, best estimates and 95% confidence intervals (CIs) for various sample sizes are presented in Table 3.

	Sample Size		
% of Participants with AEs	10	20	
5%	38.1% (0%, 38.1%)	24.7% (0.1%, 24.9%)	
20%	53.1% (2.5%, 55.6%)	37.9% (5.7%, 43.7%)	
35%	60.4% (9.3%, 69.6%)	43.8% (15.4%, 59.2%)	
50%	62.6% (18.7%, 81.3%)	45.6% (27.2%, 72.8%)	
65%	60.4% (30.4%, 90.7%)	43.8% (40.8%, 84.6%)	
80%	53.1% (44.4%, 97.5%)	37.9% (56.3%, 94.3%)	
95%	38.1% (61.9%, 100%)	24.7% (75.1%, 99.9%)	

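### The ESRD inclusion criterion is not anchored at index, so a kidney recipient whose ESRD preceded a now-functioning graft qualifies and is pooled into the safety estimates

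*Protocol*

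**What the plan says.** Section 6.2.2 sets the renal criterion in two layers. The parent item is "Diagnosis of ESRD or severe chronic renal disease prior to the index date". Under it come two routes:

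- ESRD: "If ESRD: patient diagnosed with ESRD confirmed by an eGFR <15 mL/min".
- Severe chronic renal disease that requires dialysis, with the added condition "patient has an eGFR of 15 to <30 mL/min at index".

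The transplant criterion is "Patient has undergone SOT or HSCT before index date"; it sets no order between the transplant and the renal diagnosis. Section 6.2.3 adds: "There are no exclusion criteria for this study". The current transplant types listed in Section 6.4.4 include "Kidney transplant".

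Three other places describe the intended population. Section 4 states the evidence gap as patients with "either an eGFR <15 mL/min or an eGFR <30 mL/min receiving peritoneal dialysis or hemodialysis". Section 6.2.1 speaks in the present tense of adults who have comorbid ESRD or dialysis-requiring severe renal disease. Section 6.5 describes the source population as having a "post-transplant diagnosis of comorbid ESRD" or of comorbid severe disease.

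**The concern.** One route is tied to renal function at index and the other is not. Read literally, the ESRD route asks for a diagnosis at some point before index and one confirming eGFR of unstated date. In a transplant population that matters, because ESRD is a common-sense reason for a kidney graft and a working graft reverses the condition that the study is about.

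The study exists to fill one item of missing information in the EU Risk Management Plan: safety in patients exposed to maribavir while their renal function is very poor. A patient with recovered function during exposure does not inform that item. With a target of about 10 patients, each one is about a tenth of the cohort.

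**Working it through.** **1. Literal test of Section 6.2.2.** Take an adult with ESRD (eGFR <15 mL/min) before a kidney transplant, a working graft with eGFR of 30 or more and no dialysis at index, refractory CMV after that transplant, and maribavir started in the eligibility period.

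| Requirement | Met? |
|---|---|
| Age 18 or over at index | Yes |
| ESRD diagnosed before index | Yes |
| Diagnosis confirmed by eGFR <15 | Yes, by the pre-transplant value |
| SOT or HSCT before index | Yes |
| Refractory CMV in the latest post-transplant period | Yes |
| At least one dose of maribavir in routine practice | Yes |
| Consent, where required | Assumed |
| Exclusions | None exist |

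The patient qualifies. So would a patient with past ESRD, an eGFR of 15 to <30 at index and no dialysis, whom the second route would refuse.

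The lead-in to Section 6.2.2 says that attributes must be documented in the record at enrolment. That governs what is on file, not renal status on the index date. Section 6.4.3 records the eGFR at ESRD diagnosis, which is a value a site could reasonably take as the confirmation.

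**2. The same patient against the other descriptions.**

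| Place | Condition | Met? |
|---|---|---|
| Section 4 | eGFR <15, or <30 on dialysis | No |
| Section 6.2.1 | Has comorbid ESRD or dialysis-requiring severe disease | No |
| Section 6.5 | Renal diagnosis made after transplant | No |

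**3. What happens to the patient in the analysis.** Section 6.1 has sites include eligible patients consecutively until the target is met, so this patient can use one of about 10 places. Section 6.7.1.1 defines the evaluable safety population by at least one dose, and Section 6.7 pools all sites. Subgroup analyses are optional. Section 6.4.4 collects eGFR, disease stage and dialysis status at index, but no eligibility or analysis rule uses them.

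**4. Size.** The method was first checked against the plan's own figures. Exact (Clopper-Pearson) 95% limits with x = n × p, non-integer x allowed, reproduce all 14 cells of Table 3 to 0.1 percentage point; for example n = 10 at 50% gives 18.7% to 81.3%, width 62.6 points.

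The number k of off-target patients among 10 is not in the documents, so it is varied as an assumption. The patients who inform the question number m = 10 − k. For an adverse event seen in none of them, the exact upper limit is 1 − 0.025^(1/m):

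| k | m | Upper limit, 0 events | 95% CI width at 50% |
|---|---|---|---|
| 0 | 10 | 30.8% | 62.6 points |
| 1 | 9 | 33.6% | 65.4 points |
| 2 | 8 | 36.9% | 68.6 points |
| 3 | 7 | 41.0% | 72.2 points |
| 5 | 5 | 52.2% | 81.1 points |

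For example, m = 8 gives 1 − 0.025^(1/8) = 0.369. No assumed event risk enters the zero-event column.

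**The case against.** The best defence is that the intent is plain. The title, the objectives and Section 6.2.1 all say comorbid ESRD, and Section 6.5 adds a post-transplant diagnosis. A careful site could apply that intent and refuse the patient above. Such a patient would also not be hidden: index eGFR, dialysis status, and the dates of ESRD diagnosis and current transplant are all collected, Section 6.7.1 summarises the Section 6.4 variables, and Section 6.7.1.1 promises individual listings and narratives. In a cohort of about 10, an index eGFR of 30 or more would be noticed.

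This stands as mitigation and not as a cure. Sites screen against the listed criteria, and by writing the index condition into one route only, Section 6.2.2 invites the reading that the other route has none. Disclosure does not take the patient out of the pooled numerator and person-time.

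A reader might go further and infer that such patients are easier to find and would fill most of the places, or that the pooled event proportion would shift by a particular amount. The documents support neither. They give no count or share of these patients, and no event risks by level of renal function from which a shift could be computed. Nor does it follow that the report would necessarily claim evidence it lacks, since the baseline tables and listings would show the index values.

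**Conclusion.** The point holds. As written, the ESRD route is a faulty eligibility rule and not merely a missing detail: it admits patients whom Sections 4, 6.2.1 and 6.5 do not describe, and the analysis counts them. That conclusion rests on the wording alone.

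The natural reading is that the confirming eGFR may come from any time before index, because the diagnosis must precede index; strictly, the text gives no date at all. How often the gap would matter cannot be derived. The loss of information is conditional on the assumed k: with 2 of 10 off-target, the upper limit for an unseen event moves from 30.8% to 36.9%, and with 5 of 10 to 52.2%.

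**What to change.** - In Section 6.2.2, apply the ESRD route's existing eGFR threshold of <15 mL/min at index, as the other route already does for its own range. The sponsor should set a look-back window for the qualifying value; without one, an old value could still qualify.
- If a dialysis route is mentioned for ESRD, keep it within the eGFR limit of <30 that Section 4 attaches to dialysis. Dialysis at any eGFR would widen the population and make the second route's range redundant.
- Reconcile the post-transplant diagnosis wording in Section 6.5 with Section 6.2.2. The documents do not settle which governs, so the sponsor must decide whether timing relative to the transplant matters in addition to status at index.
- Add an eCRF check of eligibility against the index eGFR and dialysis status already collected under Section 6.4.4.

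The cost is a few lines of text and one edit check, with no new variables. The drawback is real but limited: variables depend on what the chart holds (Section 6.4), and information absent from the record will not be queried (Section 6.8.1), so a true ESRD patient with no eGFR near index could be lost. With a target of about 10, the look-back window should be chosen with that in mind, and the screening log foreseen in Section 6.9 could record such losses.
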